Alpha-1 (α 1)-blockers decrease smooth muscle tone in the prostate, thereby rapidly improving urinary symptoms and flow. Currently available α 1-blockers include the selective α 1-blockers terazosin, doxazosin and alfuzosin and the highly selective α 1A-blocker tamsulosin and silodosin. These agents have comparable efficacy, and the major differences between these agents are their tolerability profiles. (*Montorsi and Moncada, 2006*).

All these agents produce their effects on voiding within hours of administration, regardless of prostate size without altering serum prostate specific antigen (PSA) or volume (*Irani, 2006*)

The alpha(1A)- and alpha(1D)-adrenoceptor antagonist tamsulosin, given at a dosage of 0.4 mg once daily in a modified-release formulation, is effective and well tolerated in the treatment of LUTS associated with BPH. Although the drug has been directly compared to date with one other agent only, data show overall that tamsulosin clearly offers advantages over other alpha(1)-adrenoceptor antagonists in terms of the need for a single daily dose only, and its low potential for hypotensive effects or interference with concomitant antihypertensive therapy. Dosage titration at the start of treatment is not necessary. Tamsulosin has a rapid onset of action and is effective in patients with moderate or severe symptoms. The drug is therefore a valuable therapeutic option, with both demonstrated and potential advantages over older nonselective agents, in the management of patients with LUTS associated with BPH. (*Dunn CJ et al., 2002*)

By decreasing the resistance, α 1-blockers can help relieve AUR and improve the chances of successful TWOC. (*McNeill, 2001*)

Longer catheter duration significantly increases the risk of complications such as urinary tract infections, urine leak and catheter obstruction and urethral stricture, all efforts should be

made to try to minimize the duration of catheterization and so reduce co-morbidity and healthcare costs (*Fitzpatrick et al., 2011*).

However, the optimum duration of therapy has not been fully assessed, and there is controversy regarding the length of time a catheter should remain in situ during the initial therapeutic phase. (*Kara and Yazici , 2014*)

AIM OF WORK

The aim of this work is to compare between early (3days) and late(7days) removal of urinary catheter after acute urine retention in patients with Benign Prostatic Hyperplasia under Tamsulosin treatment.

PATIENTS AND METHODS

It is a prospective randomized study that will be performed on 60 male patients with acute urinary retention(AUR) secondary to Benign Prostatic Hyperplasia(BPH) having their first attack.

All patients will be catheterized and the urine volume will be assessed and subjected to culture and sensitivity tests. After catheter insertion, the patients will receive prophylactic dose of levofloxacin 500 mg once and they will be divided randomly into two groups:

Group I: 30 patients will receive Tamsulosin hydrochloride 0.4 mg once daily and the catheter will be removed after 3 days.

Group II: 30 patients will receive Tamsulosin hydrochloride 0.4 mg once daily and the catheter will be removed after 7 days.

Exclusion criteria:

- 1) Renal impairment.
- 2) Suspected urethral stricture.
- 3) Neurogenic bladder.
- 4) Cancer prostate.
- 5) Medically induced retention.
- 6) Previous use of alpha blockers.
- 7) History of drug hypersensitivity or allergy to Tamsulosin.
- 8) Chronic retention.

Inclusion criteria:

Patients having first attack of acute urinary retention secondary to BPH.

Patients Evaluation:

- 1) All patients will be subjected to complete medical history with stress on lower urinary tract symptoms (LUTS) before acute urine retention (AUR) using International Prostate Symptom Score (IPSS) .
- 2) Detailed past medical and operative history will be taken.
- 3) Complete physical examination will be carried out including Digital Rectal Examination (DRE).
- 4) All patients will be subjected to Pelvi-Abdominal Ultrasound and estimation of prostate size.
- 5) Follow up :
 - A. Complications related to catheter such as hematuria, obstruction, Urinary leakage and urinary tract infections will be recorded in the two groups.
 - B. After catheter removal, patients will be allowed to void and will be discharged home who will have a successful void more than 200 cc of urine. Patients who will fail to void will be re-catheterized and will be prepared for prostatectomy.
 - C. Two weeks after catheter removal :
 - All patients will be subjected to:
 - Pelvi-abdominal ultrasound with estimation of post voiding residual urine .
 - Uroflowmetry.
 - Urine analysis ,urine culture and sensitivity tests.
 - Prostatic specific antigen (PSA).
 - D. Six weeks after catheter removal:

- The previous investigation will be repeated.

Statistical Methods:

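### The plan does not say that anyone assessing outcomes is masked, although the week-2 and week-6 residual-urine and uroflow readings could be taken without knowledge of the arm at low cost

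*Combined protocol and SAP*

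**What the plan says.** Patients and Methods opens with the only description of the design: "It is a prospective randomized study that will be performed on 60 male patients". Allocation follows catheterization, and all that is said of it is that "they will be divided randomly into two groups". Both arms get the same tamsulosin treatment, 30 men in each, and they differ only in when the catheter comes out: day 3 in Group I and day 7 in Group II.

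Under Patients Evaluation, item 5 (Follow up), part A records catheter complications. Part B is the voiding trial at removal, with success set at more than 200 cc; men who fail are re-catheterized and prepared for prostatectomy. Part C begins "C. Two weeks after catheter removal" and lists "Pelvi-abdominal ultrasound with estimation of post voiding residual urine", along with a flow test, urine tests and PSA. Part D, at six weeks, says "The previous investigation will be repeated".

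Statistical Methods plans an unpaired t-test for numerical variables, with significance at P below 0.05. Neither section says who performs or reads any test, what that person knows about the arm, or how a residual volume is measured or a flow trace accepted.

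**The concern.** Residual urine and flow are the only measured voiding-function outcomes listed after discharge. The plan itself calls the residual volume an estimation and sets no procedure for it, so the operator's judgement can enter the number. Uroflowmetry is an instrument reading. Judgement enters it less, mainly through how the test is run, which trace is accepted and how artefact is handled.

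If the person making these judgements knows the arm, a systematic lean goes straight into the difference between arms. The planned t-test has no means of detecting or removing it.

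The introduction argues for keeping catheterization as short as possible, so staff may well hold an expectation. That makes bias plausible; it does not show that any will occur. The point is worth raising because these particular outcomes can be protected by a small change, whereas the voiding trial and complication recording take place when the duration is plainly visible.

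**Working it through.** **1. Where masking is possible.**

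- Up to removal: the arms differ only in catheter duration, 3 against 7 days. Patients and ward staff must know it, so parts A and B cannot be masked in any simple way.
- At parts C and D: both visits are timed from each man's own removal. Men who voided attend without a catheter, 14 or 42 days after removal, in either arm. Time since removal therefore carries no information about the arm.

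**2. What could still reveal the arm.** Time since insertion is duration plus the visit interval:

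| Visit | 3-day arm | 7-day arm |
|---|---|---|
| Two weeks | 3 + 14 = day 17 | 7 + 14 = day 21 |
| Six weeks | 3 + 42 = day 45 | 7 + 42 = day 49 |

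An operator who sees the retention or insertion date can work out the arm. The patient also knows his own duration and may mention it.

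**3. Illustration of size.** The plan gives no SD, effect size, power or expected failure rate, so there is no figure to reproduce. Inputs from the plan: n = 30 per arm, unpaired t-test, alpha 0.05. Assumptions: a two-sided test, no true difference, and a reading lean of b SD between arms.

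- Degrees of freedom: 2n − 2 = 58; critical value 2.00.
- Noncentrality: b × √(n/2) = b × √15. For b = 0.2 this is 0.2 × 3.873 = 0.775.
- False-positive rate: the probability that a noncentral t variable falls beyond ±2.00.

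The calculation is repeated for 18 per arm (34 degrees of freedom, critical value 2.03, noncentrality b × √9), in case many men fail the voiding trial and are not measured. The figure of 18 is an assumption.

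| Assumed lean | 30 per arm | 18 per arm |
|---|---|---|
| 0 | 5.0% | 5.0% |
| 0.1 SD | 6.7% | 6.0% |
| 0.2 SD | 11.9% | 9.0% |
| 0.3 SD | 20.8% | 14.1% |
| 0.4 SD | 33.2% | 21.5% |

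**4. The opposite direction.** At 30 per arm, a true difference of 0.736 SD would be detected with 80% power (noncentrality 0.736 × 3.873 = 2.851). If a lean of 0.2 SD works against that difference, the apparent difference is 0.736 − 0.2 = 0.536 SD. The noncentrality is then 0.536 × 3.873 = 2.076, and the chance of detection falls to about 53%.

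**The case against.** The strongest reply is that silence is not evidence. A reader might infer from the text that nobody is masked. The documents do not say so: they do not identify the ultrasound operator or the uroflow reader, and either could already be working without knowledge of the arm. That stands, and the point is limited to masking not being stated.

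Four further objections hold in whole or in part.

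- **Cost.** One might call masked reading free. The documents say nothing about cost, and a changed form masks only an operator who did not take part in removing the catheter. Low cost is as far as one can go.
- **Visit timing.** It is tempting to say that nothing at the visit reveals the arm. Days since insertion and the patient's own account can both reveal it.
- **Size and direction.** The lean is assumed throughout. No hypothesis is stated, and the hoped-for result could be that 3 days is no worse, in which case bias would hide a difference and the false-positive rate would be the wrong measure. The rates at 30 per arm also assume every man is measured, although those who fail the voiding trial may not be assessable at parts C and D.
- **Selection.** Men measured after passing the voiding trial are a subset formed after randomization. Masked reading does nothing about that, and it should not be taken to make these outcomes sound in every respect. The voiding trial and complication recording remain at least as exposed to bias.

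None of this removes the core: the plan is silent, the readings involve some judgement, and a simple protection is available where it can work.

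**Conclusion.** The concern holds in limited form. The available text states no masking of outcome assessors. The week-2 and week-6 residual-urine estimates, and to a lesser degree the uroflow traces, could be read without knowledge of the arm, and the plan should provide for this.

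The documents do not support a claim that these outcomes will be biased, or biased toward a difference. Under the assumed 0.2 SD lean, the false-positive rate is about double the nominal 5%: 11.9% at 30 per arm and 9.0% at 18. If masked reading removes the lean, the rate returns to 5%. Sample size and alpha are unaffected. The conclusion that masking is feasible rests on the visit timing in the plan and on the readers being people who did not remove the catheter, which the plan does not settle.

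**What to change.** Add to Follow up, parts C and D:

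1. Patients and treating staff are unmasked, and so are the voiding trial and the recording of catheter complications.
2. Residual urine and uroflow are read by the existing ultrasound operator and uroflow reader, who must be staff who did not remove that patient's catheter.
3. Their request form carries the study number only, with no arm and no retention, insertion or removal date. The patient is asked not to mention how long he had the catheter.
4. Residual volume, voided volume and maximum flow are recorded before the chart is opened.
5. The results are reported as assessor-masked measurements among the men measured, with the number measured in each arm and a note that masking does not correct for men lost through a failed voiding trial.

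The cost is low: a changed form and a few sentences of text. No second reader, visit or procedure is asked for, and patient management is unchanged. The small downside is imperfect masking, since a patient may still disclose his duration.
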